16.2 Appendix 2: Specific Renal Alert Criteria and Actions and Event Follow-up

Table 16-3 Specific Renal Alert Criteria and Actions

Serum Event	
Serum creatinine increase 25 – 49% compared to baseline	Confirm 25% increase after 24-48h Follow up within 2-5 days
Acute Kidney Injury: Serum creatinine increase ³ 50% compared to baseline	Follow up within 24-48h if possible Consider study treatment interruption Consider patient hospitalization /specialized treatment
Urine Event	
New dipstick proteinuria ≥1+	Confirm value after 24-48h
Albumin- or Protein-creatinine ratio increase ≥2-fold	Perform urine microscopy Consider study treatment interruption / or discontinuation
Albumin-creatinine ratio (ACR) ≥30 mg/g or ≥3 mg/mmol; Protein-creatinine ratio (PCR) ≥150 mg/g or >15 mg/mmol	
New dipstick glycosuria ≥1+ not due to diabetes	Blood glucose (fasting) Perform serum creatinine, ACR
New dipstick hematuria ≥1+ not due to trauma	Urine sediment microscopy Perform serum creatinine, ACR
For all renal events:	
Document contributing factors in the CRF: co-medication, other co-morbid conditions, and additional diagnostic procedures performed	
Monitor patient regularly (frequency at investigator's discretion) until either:	
Event resolution: sCr within 10% of baseline or protein-creatinine ratio within 50% of baseline, or	
Event stabilization: sCr level with ±10% variability over last 6 months or protein-creatinine ratio stabilization at a new level with ±50% variability over last 6 months.

1.1 Scope of document

The RAP documents contain detailed information to aid the production of Statistics & Programming input into the Clinical Study Report (CSR) for trial “**CKAE609X2111**”.

The Statistical analysis plan (SAP) describes the implementation of the statistical analysis planned in the protocol.

1.2 Study reference documentation

Final study protocol (v02) and site operation manual (SOM v01) are available at the time of finalization of the original Statistical Analysis Plan.

1.3 Study objectives

Objective(s)	Endpoint(s)
Primary objective(s)	Endpoint(s) for primary objective(s)

 To assess the safety and tolerability of single and multiple iv doses of KAE609 in healthy subjects 	
 Adverse events, physical examination findings, vital signs, ECG findings (including QTcF), safety laboratory assessments including chemistry, hematology, and urinalysis results
Secondary objective(s)	Endpoint(s) for secondary objective(s)

 To assess the pharmacokinetics (PK) of single and multiple iv doses of KAE609 in healthy subjects To assess local tolerance at infusion site of KAE609 iv administration 	
 AUC, Tmax, Cmax, CL, Vz, and T1/2 Findings of physical examination of infusion site

Commercially Confidential Information

1.4 Study design and treatment

This is a randomized, subject and investigator-blinded, placebo-controlled, single and multiple ascending iv dose study in healthy subjects. The study consists of two parts and the study scheme is shown in [Figure 1-1](#):

- Part A is a single ascending dose (SAD) study with 5 cohorts of 8 subjects each
- Part B is a multiple ascending dose (MAD) study with 2 cohorts of 9 subjects each

For both parts of the study, each subject will participate in an up to 28- day screening period during which a full physical examination, medical history, drug screening, vital signs, ECG evaluation and safety laboratory tests evaluation will be performed.

A review of safety and PK data will be conducted at the completion of each cohort prior to dosing of the next subsequent cohort. Safety assessments will include physical examinations, ECGs, vital signs, standard clinical laboratory evaluations (hematology, blood chemistry, urinalysis) adverse event and serious adverse event monitoring.

Commercially Confidential Information

Part A: Single-ascending dose study

In Part A sequential cohorts of 8 healthy subjects per cohort will be randomized to receive successively higher single iv doses of KAE609 or matching placebo. In each cohort, subjects will be randomized in a 3:1 ratio to KAE609 (6 subjects/cohort) or matching placebo (2 subjects/cohort). Four planned dose cohorts will be included in Part A (A1, A2, A3 and A4).

Commercially Confidential Information

Commercially Confidential Information

Figure 1-2 Study design - SAD

Commercially Confidential Information

Part B: Multiple-ascending dose study

In Part B sequential cohorts of 9 healthy subjects per cohort will be randomized to receive successively higher iv doses of KAE609 or matching placebo. Two planned dose cohorts will be included in Part B (B1 and B2). For Cohort B1, healthy subjects will receive a 60 mg dose of KAE609 or matching placebo iv q24h for 5 days. . For Cohort B2, healthy subjects will receive a 120 mg dose of KAE609 or matching placebo iv q24h for 5 days. In each cohort, subjects will be randomized in a 2:1 ratio to KAE609 (6 subjects/cohort) or matching placebo (3 subjects/cohort).

Commercially Confidential Information

Commercially Confidential Information

Figure 1-3 Study design - MAD

Commercially Confidential Information

2 First interpretable results (FIR)

Commercially Confidential Information

3 Interim analyses

Commercially Confidential Information

4 Statistical methods: Analysis sets

For subjects for which the actual treatment received does not match the randomized treatment, the treatment actually received will be used for the analysis.

The safety analysis set will include all subjects who received at least one dose of any study drug. The PK analysis set will include all subjects with at least one available valid (i.e. not flagged for exclusion) PK concentration measurement, who received any study drug and experienced no protocol deviations with relevant impact on PK data.

The analysis sets and protocol deviation codes are related as follows:

Table 4-1 Protocol deviation codes and analysis sets

Category Deviation code	Text description of deviation	Data exclusion
Subjects are excluded from PK analysis in case of these PDs:		
TRT01	Incorrect dose administered	Exclude subject from PK analysis set at pharmacokineticist discretion

If updates to this table are needed, an amendment to the SAP needs to be implemented prior to DBL.

5 Statistical methods for Pharmacokinetic (PK) parameters

The secondary objective is to evaluate the pharmacokinetics of single and multiple ascending iv doses of KAE609 in healthy subjects.

5.1 Variables

The pharmacokinetic parameters are described as follows and will be calculated separately from the KAE609 concentration data:

- Part A (SAD): C_{max}, T_{max}, AUC_{last}, AUC_{inf}, AUC_{0-t} (AUC₀₋₂₄), T_{1/2}, V_{ss} and CL
- Part B (MAD): C_{max}, T_{max}, AUC_{0-24h}, T_{1/2} Day 1 and C_{max}, T_{max}, AUC_{tau} (AUC₀₋₂₄), AUC_{last}, T_{1/2}, V_{ss} and CL

5.2 Descriptive analyses

For each part, KAE609 plasma concentration data will be listed by subject, and visit/sampling time point. Descriptive summary statistics will be provided by treatment and visit/sampling time point, Commercially Confidential Information

Summary statistics will include mean (arithmetic and geometric), SD, CV (arithmetic and geometric), median, minimum and maximum. Commercially Confidential Information

PK parameters will be listed by subject. Descriptive summary statistics will include mean (arithmetic and geometric), SD, and CV (arithmetic and geometric), median, minimum and

maximum. An exception to this is Tmax where median, minimum and maximum will be presented.

5.3 Statistical model, assumptions and hypotheses

Commercially Confidential Information

5.3.1 Model checking procedures

Graphical check will be performed.

5.3.2 Graphical presentation of results

Arithmetic mean (SD) plasma concentration data will be plotted across time, with separate line types for each treatment.

Overlying individual plasma concentration-time profiles will be generated.

Scatterplots of Cmax and AUC parameters versus dose will be created with the estimated power model curve overlaid.

6 Statistical methods for Pharmacodynamic (PD) parameters

Not applicable.

7 Statistical methods for safety and tolerability data

The primary objective of this study is to assess the safety and tolerability of single and multiple ascending iv doses of KAE609 in healthy subjects.

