Part A: Single-ascending dose study

In Part A sequential cohorts of 8 healthy subjects per cohort will be randomized to receive successively higher single iv doses of KAE609 or matching placebo. In each cohort, subjects will be randomized in a 3:1 ratio to KAE609 (6 subjects/cohort) or matching placebo (2 subjects/cohort). Five planned dose cohorts will be included in Part A (A1, A2, A3, A4 and A5). Provisional dose levels are described in [Section 6.5.1.2](#).

Commercially Confidential Information

For a detailed outline of safety and other assessments, please refer to Part A Assessment Schedule ([Table 8-1](#)). If added, any additional dose cohort will follow the same Part A [Assessment Schedule](#).

Figure 3-2 Study design - SAD

Commercially Confidential Information

Part B: Multiple-ascending dose study

In Part B sequential cohorts of 9 healthy subjects per cohort will be randomized to receive successively higher iv doses of KAE609 or matching placebo. Two planned dose cohorts will be included in Part B (B1 and B2). For Cohort B1, healthy subjects will receive a 60 mg dose of KAE609 or matching placebo iv q24h for 5 days. For Cohort B2, healthy subjects will receive a 120 mg dose of KAE609 or matching placebo iv q24h for 5 days. In each cohort, subjects will be randomized in a 2:1 ratio to KAE609 (6 subjects/cohort) or matching placebo (3 subjects/cohort). Provisional dose levels are described in [Section 6.5.1.2](#)

Commercially Confidential Information

For a detailed outline of safety and other assessments, please refer to Part B Assessment Schedule ([Table 8-2](#)). Any additional cohort will follow the same Part B [Assessment Schedule](#).

Figure 3-3 Study design - MAD

Commercially Confidential Information

4 Rationale

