6.7 Preparation and dispensation

Each study site will be supplied with study drug in packaging as described under the investigational and control drugs section (Section 6.1.1).

KAE609 will be administered to the subject at the study center via the following route of administration:

- iv bolus administration over approximately 2 min (cohorts A1, A2 and B1)
- iv infusion over approximately 10 min (cohorts A3, A4, A5 and B2)

Depending on emerging data of this study infusion duration might be adapted (for example infusion over 10 min instead of bolus injection).

See the SOM and Pharmacy Manual for further details.

7 Informed consent procedures

Eligible subjects may only be included in the study after providing (witnessed, where required by law or regulation), IRB/IEC-approved informed consent.

Informed consent must be obtained before conducting any study-specific procedures (e.g. all of the procedures described in the protocol). The process of obtaining informed consent must be documented in the subject source documents.

Novartis will review the investigators/CRO proposed informed consent form to ensure it complies with the ICH E6 GCP guidelines and regulatory requirements and is considered appropriate for this study. Any further changes to the proposed consent form suggested by the investigator must be agreed to by Novartis before submission to the IRB/IEC.

Information about common side effects already known about the investigational drug can be found in the Investigator's Brochure. This information will be included in the subject informed consent and should be discussed with the subject during the study as needed. Any new information regarding the safety profile of the investigational drug that is identified between Investigator's Brochure updates will be communicated as appropriate, for example, via an investigator notification or an aggregate safety finding. New information might require an update to the informed consent and then must be discussed with the subject.

Male subjects must be informed that if a female partner becomes pregnant while he is enrolled in the study, contact with the female partner will be attempted to request her consent to collect pregnancy outcome information.

Commercially Confidential Information

A copy of the approved version of all consent forms must be provided to Novartis/sponsor after IRB/IEC approval.

Refer to the SOM for a complete list of ICFs included in this study.

8 Visit schedule and assessments

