Assessment schedule lists all of the assessments and indicates with an “X”, the visits when they are performed. All data obtained from these assessments must be supported in the subject’s source documentation.

Subjects should be seen for all visits/assessments as outlined in the assessment schedule or as close to the designated day/time as possible. Missed or rescheduled visits should not lead to automatic discontinuation. Subjects who prematurely discontinue the study for any reason should be scheduled for a visit as soon as possible, at which time all of the assessments listed for the EOS visit will be performed. At this EOS visit, the adverse event and concomitant medications should be recorded on the CRF.

Specification and timing of each assessment are detailed in the protocol. The methods and recording of each assessment may be outlined in the SOM.

Epoch	Screening		Treatment Period										Post-Treatment Follow-Up					Post Study	
Visit Name	Screening	Baseline	Treatment										Follow-up				EOS	Safety Contact	
Days	-29 to -2	-1	1										2	3	4	6	8	30	
Time (post-dose)	-	-	-1h ¹	0h	2min ²	10min	30min	1h	3h	4h	6h	12h	24h	48h	72h	120h	-	-	
12 lead Holter continuous ECG ⁸			X																
ECG evaluation ⁴	X	X	X			X	X	X	X		X	X	X				X		
Blood Pressure and Pulse Rate	X	X	X			X	X	X	X				X		X		X		
Drug administration record ⁷				X															
Injection/infusion site observation			X		X		X												
Blood chemistry	X	X											X		X		X		
Hematology	X	X											X		X		X		
Urinalysis	X	X											X				X		
PK blood collection			X		X	X	X	X	X		X	X	X	X	X	X	X		
CCI			X																
CCI			X																
Inpatient			X																
Concomitant medications	X ¹⁰																		
Adverse events/serious adverse events	X ¹⁰																		

Epoch	Screening		Treatment Period										Post-Treatment Follow-Up					Post Study	
Visit Name	Screening	Baseline	Treatment										Follow-up				EOS	Safety Contact	
Days	-29 to -2	-1	1										2	3	4	6	8	30	
Time (post-dose)	-	-	-1h ¹	0h	2min ²	10min	30min	1h	3h	4h	6h	12h	24h	48h	72h	120h	-	-	
Study completion information																		X	
Safety Follow up Call																			S

^X Assessment to be recorded in the clinical database or received electronically from a vendor

^S Assessment to be recorded in the source documentation only

¹ Pre-dose

² Only collected/done in cohorts with bolus injection.

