8.4.2 Electrocardiogram (ECG)

For Part A, triplicate ECGs will be collected at screening, baseline, and at Day 8 (EOS). At other times, single ECGs will be collected at all times when PK samples are collected (ECG is not needed at 2 min).

For Part B, triplicate ECGs will be collected at screening, baseline, Days 3, 4, and Day 12 (EOS). At other times, single ECGs will be collected at all times when PK samples are collected (ECG is not needed at 2 min).

All ECGs will be measured after a 10 min rest in the supine position. The following parameters will be reported : PR interval, QRS duration, heart rate, RR interval, QT interval, QTcF.

The Fridericia QT correction formula (QTcF) must be used for clinical decisions.

As applicable, QTcF and QTcB may be calculated at the site. Unless auto-calculated by the ECG machine, the investigator must calculate QTcF at the Screening and/or Baseline visit(s) (as applicable) to assess eligibility and continuation in the study.

Clinically significant abnormalities must be recorded on the relevant section of the medical history/Current medical conditions/AE eCRF as appropriate.

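### Within each part, administration mode changes with dose, so the Cmax-versus-dose curve in SAP 5.3.2 should show mode and be read with that limit

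*SAP*

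**What the plan says.** The plotting instruction in SAP 5.3.2 reads: "Scatterplots of Cmax and AUC parameters versus dose will be created with the estimated power model curve overlaid". SAP 5.3, which would define the model, is redacted, as are parts of Protocol 12.5.1 and all of Protocol 12.6. SAP 5.3.1 plans only a graphical check of the model.

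Protocol 6.7 sets two modes of administration: "iv bolus administration over approximately 2 min (cohorts A1, A2 and B1") and "iv infusion over approximately 10 min (cohorts A3, A4, A5 and B2"). It adds: "Depending on emerging data of this study infusion duration might be adapted".

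Doses rise within each part. In Protocol section 3, Part A subjects are "randomized to receive successively higher single iv doses of KAE609 or matching placebo". For Part B the same section says: "For Cohort B1, healthy subjects will receive a 60 mg dose of KAE609 or matching placebo iv q24h for 5 days". Cohort B2 receives 120 mg on the same schedule.

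The assessment schedule has PK samples at 2 and 10 minutes post-dose. Its footnote 2 says of the 2-minute time: "Only collected/done in cohorts with bolus injection". Protocol Table 12-1 defines Cmax as the maximum observed concentration.

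**The concern.** Observed Cmax after an intravenous dose depends on how fast the drug goes in. When concentration falls once input stops, a 10-minute input gives a peak no higher than a 2-minute input of the same dose, and a lower one if early distribution is fast. In each part the lower doses are given fast and the higher doses slowly. A single Cmax curve fitted across both modes therefore takes some of the mode effect into its slope, and the drug looks less than dose-proportional.

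The study is meant to guide dose selection for later trials, so a mode effect read as a dose effect would mislead. AUC does not share the problem: under linear kinetics it depends on dose and clearance, not on whether input took 2 or 10 minutes.

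**Working it through.** The plan states no figure for this output, so there is none to reproduce. The check asks how far mode and dose overlap, and what that does to the slope.

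**Inputs from the documents.** Mode by cohort (Protocol 6.7); dose order in Part A and 60 versus 120 mg in Part B (Protocol section 3); 6 active subjects per cohort (Protocol 12.8.1).

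**Assumed, because the documents do not show them.** Part A dose spacing (doubling), early kinetics, CV, and a log-log power model with true slope 1.

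**Overlap of mode and dose, Part A.** Code the five log doses as -2, -1, 0, 1, 2 and mode as 0, 0, 1, 1, 1. The cross-product is 0 + 1 + 2 = 3, the sum of squares of log dose is 10, and that of mode is 5 × 0.6 × 0.4 = 1.2.
- r² = 3²/(10 × 1.2) = 0.75, for any equal log step.
- Slope bias = (3/10) × ln(R)/ln(step), where R is infusion Cmax over bolus Cmax at equal dose. For doubling doses this is 0.300 × log2(R).
- The SE of the slope rises by 1/√(1 - 0.75) = 2.0 when mode is fitted.

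**Overlap in Part B.** There are two cohorts, one per mode, so dose and mode are fully aliased. Under proportional kinetics the B2/B1 Cmax ratio is 2R and the apparent exponent is 1 + log2(R).

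**Range of R.** Take a biexponential profile with a slow half-life of 24 h, a fast phase holding 30-80% of the initial concentration, and a fast half-life of 2-30 min. At the end of an input lasting T, each phase contributes its fraction × (1 - exp(-kT))/(kT).

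Example with a 50% fast fraction and a 10-min fast half-life:
- T = 2: 0.5 × 0.934 + 0.5 × 0.9995 = 0.967
- T = 10: 0.5 × 0.721 + 0.5 × 0.998 = 0.859
- R = 0.859/0.967 = 0.89

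| Sampling assumption | R | Pooled Part A slope, 1 + 0.300 × log2(R) |
|---|---|---|
| End of dosing, both modes | 0.545-0.973 | 0.74-0.99 |
| Example above | 0.89 | 0.95 |
| No fast phase | 0.998 | 0.999 |
| Bolus +2 min, infusion +10 min after end of dosing | 0.421-0.927 | 0.63-0.97 |
| Bolus +2 min, infusion at end of dosing | 0.867-0.987 | 0.94-0.99 |

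**Dose spacing.** At R = 0.80 the bias is -0.17, -0.10 and -0.06 for 1.5-, 2- and 3-fold steps.

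**Number of cohorts.** One sentence of SAP 1.4 lists four Part A cohorts, although its design bullet and Protocol section 3 say five. With A1-A4 only, r² = 0.80, and end-of-dosing sampling gives slopes of 0.65-0.98.

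**Part B.** At R = 0.89 the B2/B1 ratio would be 2 × 0.89 = 1.78 and the apparent exponent 0.83, for a drug that is truly proportional.

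**Precision of an adjusted Part A slope.** Residual SD = √ln(1 + CV²), which is 0.198 at CV 20% and 0.294 at CV 30%. The pooled SE is SD/√(6 × 10 × (ln 2)²) = SD/5.37, giving 0.037 and 0.055. Fitting mode doubles these to 0.074 and 0.109.

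**The case against.** The strongest objection is the redaction. The curve comes from a model whose whole section is blacked out. A mode term, or a fit restricted to one mode, could be stated there. This stands: a reader might infer that the SAP pools across modes, but the documents do not show it. The plotting sentence is visible, however, and asks for no marking by mode.

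A reader might also infer that Cmax is captured on unequal sampling grids, because only bolus cohorts have a 2-minute sample. The documents do not establish this. If times run from the start of dosing, the 2- and 10-minute samples fall at the end of the bolus and of the infusion respectively, and the grid fits the modes. The schedule says only post-dose and leaves the origin open.

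Plot symbols alone add little while the plan is followed, since each cohort has one dose and one mode. They matter if duration is adapted, as Protocol 6.7 allows, or if the parts share a plot. An adaptation that brought all cohorts to one duration would remove the problem.

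Other visible outputs help the reader: individual concentration-time profiles, Tmax summaries and listings of drug administration. None of them corrects a fitted slope.

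Finally, the adjusted slope is less precise, and where R is near 1 the pooled slope is the better estimate. That is why adjustment is proposed only as a sensitivity result.

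**Conclusion.** The point holds as a minor one. The confounding of mode with dose within each part is established from visible text. A downward bias in the Cmax slope follows if the curve is fitted across modes. Its size is not fixed by the documents: negligible with no fast distribution phase, and a slope of about 0.74 to 0.99 instead of 1.0 under the assumed kinetics, five doubling doses and end-of-dosing sampling. These are ranges over assumed values, not estimates for this drug.

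Two wider readings are not supported. Bolus at lower doses and infusion at higher doses is confirmed only within a part; the Part A doses are redacted, so the ordering across parts is unknown. Nor is the plot shown to drive dose escalation. Protocol 4.2 wants AUC and Cmax kept within limits, but that is the between-cohort review. The plot is descriptive, with no visible test or decision rule attached.

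**What to change.** Leave AUC as planned. For Cmax:

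1. In SAP 5.3.2, mark points by the mode actually received, not the planned mode.
2. For Part A, report a slope with a fixed effect for mode as a sensitivity result beside any pooled slope. It can be estimated because each mode covers more than one dose, assuming a common slope.
3. State that B1 versus B2 Cmax cannot separate dose from mode, so a less-than-proportional rise between them is not attributed to dose alone.

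If the redacted model text already handles mode, only the first item is needed.

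The cost is plot symbols, one extra result row and one sentence. The downside is precision: with five cohorts the adjusted slope has about twice the SE of the pooled one (0.074 versus 0.037 at CV 20%, 0.109 versus 0.055 at CV 30%), and the text should say so. No change to dosing or sampling is implied.
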